### **9.1.4 Bone marrow harvest**

Bone marrow will be harvested from the patient under general anaesthesia from the posterior iliac crests on both sites by multiple punctures. Marrow will be collected into sterile bags containing ACD (acid citrate dextrose) (Baxter). The amount of marrow collected will be equivalent to 20 ml/kg of body weight. The risks of the procedure include the standard risks of general anaesthesia and complications associated with the bone marrow harvest procedure. The latter include pain at the site of puncture following the procedure, excessive blood loss resulting in anaemia and the potential for infection at the puncture site. The anaesthetic risks will be minimised by the anaesthetic being administered by a paediatric anaesthetist at a major paediatric tertiary referral centre. The patient will be given paracetamol pain relief after the

procedure and will be monitored carefully to check haemodynamic status. It is likely that the patient will need a blood transfusion after the bone marrow harvest. Infection risk will be minimised by careful cleansing of the site prior to needle insertion and strict adherence to sterile technique during the procedure.

### **9.1.5 Peripheral blood stem cell harvest**

Treatment of patients or donors with granulocyte colony stimulating factor (G-CSF) and Plerixafor results in the mobilisation of bone marrow stem and progenitor cells into the peripheral blood, from where they can be harvested. The quality of cells collected in terms of engrafting potential has been such that many centres have virtually replaced transplantation of bone marrow with that of peripheral blood stem cells (PBSCs) particularly in the autologous setting. The advantages of this procedure (over bone marrow harvest) are that a larger number of stem cells can be harvested, and no anaesthetic is required. G-CSF is administered by subcutaneous injection for 6 days. On day 5, Plerixafor may also be administered by subcutaneous injection. The commonest side effect is of bone and muscle pain, which is easily controlled with mild analgesics. Rare reports (<1 in 1000 patients) exist of allergic-type reactions (including anaphylaxis, skin rash, urticaria, angioedema, dyspnoea and hypotension), usually when the drug has been injected intravenously. Temporary abnormalities of liver function and skin rashes have occurred in a very small number of patients, usually on long term therapy for neutropenia. Apart from extremely rare reports of spontaneous splenic rupture, the safety records of both G-CSF and Plerixafor are very good. If patients develop unanticipated inflammatory reactions, which in the opinion of the investigator are due to G-CSF and/or to Plerixafor toxicity, then administration will be terminated and the patient would then be proposed a bone marrow harvest.

After mobilisation, the cells are harvested by leukapheresis on two consecutive days from centrally placed cannulae. Each leukapheresis lasts from three to four hours and has been shown to be extremely safe both in adults and in children. Adverse reactions to apheresis procedures are rare, although vasovagal episodes related to needle insertions or transient volume loss can occur. The former reaction is prevented by lying down and if necessary, fluid administration. Paraesthesiae or tingling can also sometimes occur due to lowering of calcium levels by the citrate anticoagulant. This is readily relieved by slowing the rate or temporarily interrupting the anticoagulant infusion. The precautions taken to minimise pain, haematoma formation, risk of infection at needle site and vasovagal fainting are outlined above. Leukapheresis can be associated with some loss of red blood cells and plasma equivalent to 100 to 200 ml of whole blood though every effort will be made to keep this volume as low as possible. Insertion of the apheresis line can lead to occlusion of blood flow and therefore can result in thrombus formation. This is treated with anti-coagulant and regular screening to

monitor reduction of the size of the thrombus. Leukapheresis is a routine procedure with minimum side effects or complications. Potential complications include formation of haematoma at the site and a small risk of infection as with any intravenous catheter.

### **9.1.6 CD34+ cell infusion**

Based on results from other gene transfer studies and our own experience, the infusion of cultured and gene altered autologous blood progenitors does not appear to be associated with any significant reactions. In this study, the medium used to culture the CD34+ cells is free of animal serum. However, infusion of any type of blood cell product can be associated with reactions resulting from clumping of these cells or other immediate reactions related to sticking of these cells to blood vessels in the lungs. Patients will be monitored as per national and hospital Blood product administration policy. Reactions are treated by stopping the infusion and providing oxygen, antihistamines, steroids and medications or fluids to increase blood pressure. Because infused cells in this study are autologous CD34+ cells, the possibility that this type of agglutination or vascular reaction will occur is very low. It is theoretically possible for the CD34+ cell cultures to become contaminated with microorganisms. One of the important safety features of this gene therapy protocol is that CD34+ cells will be cultured in a sealed bag culture system or in flasks in an isolator unit. Routine cultures will be performed on cell samples before infusion. Only interim sterility results will be available before infusion of cells. If significant growth of pathogenic microorganisms is detected, the cells will be returned with appropriate antibiotic cover, or if the infection significantly affects cell viability, the cells will not be returned to the patient.

## **9.2 Risks associated with the use of lentiviral vector**

### **9.2.1 Insertional mutagenesis**

Currently, there have been no reported cases of insertional mutagenesis in clinical trials using a lentiviral vector for gene therapy. A number of studies both in vitro and in vivo (Modlich et al., 2009; Modlich et al., 2006; Montini et al., 2006) showed that the risk for insertional mutagenesis is less genotoxic with lentiviral vectors that lack strong retroviral LTR and may be further reduced with improved vector designs.

Risks from insertional mutagenesis have occurred in clinical trials of gene transfer using retroviral vectors. After immune reconstitution in 9 of 10 subjects participating in an X-SCID gene transfer study in Paris, France, four of these subjects developed leukaemia  $\geq 2\frac{1}{2}$  years after receiving the gene-transduced CD34+ cells (Hacein-Bey-Abina et al., 2003; Hacein-Bey-Abina et al., 2008). In a similar trial of gene therapy for X-SCID performed in London, England, one of 10 subjects also developed T cell leukaemia (Howe et al., 2008). One of these five patients who developed T cell leukaemia has died and the other four are in leukaemia

remission and continue to have restored immunity from the gene therapy. For three of the subjects with leukaemia, the proviral insertion sites have been mapped within or near (3 kb) of the LMO-2 gene, a human proto-oncogene associated with T-cell leukaemia. In a fourth case, two integrations sites were described: LMO-2 and BMI1, which is also a proto-oncogene. In a fifth subject, vector had integrated near a third proto-oncogene, CCND2 (Hacein-Bey-Abina S et al., 2008). These are the first reported cases of leukaemia developing in subjects participating in a clinical study of retroviral-mediated gene transfer to CD34+ cells. The probability of leukaemia developing in other participants of the French trial, or in participants of other trials, is not known. Similarly in a trial of gene therapy for X-CGD, 2 patients developed a myelodysplasia and an acute myeloid leukaemia as result of vector mediated integration events disrupting expression of the MDS-EVI1 oncogene ((Ott et al., 2006; Stein et al., 2010)).

### **9.2.2 Replication-competent lentivirus (RCL) exposure**

Generation of RCL is highly unlikely due to the multiply deleted nature of the vector and SIN configuration, and has not been noted in any preclinical study with similar vectors. Lentiviral supernatant and patient samples will however be tested for the presence of RCL by cell culture and PCR methodology. Patient samples will be tested at time points 0 (pre-treatment), 3 months, 6 months and one year after treatment. If all tests are negative during the first year, further samples will be taken annually through-out the patient's care at GOSH and archived for at least 15 years. If in the unlikely event that post-treatment samples are positive, further analysis will be undertaken to characterize the RCL.

### **9.2.3 Germ-line transmission of vector sequences**

Issues of contraception and pregnancy are not applicable in infants and children before puberty. Because we will only be putting the EF1 $\alpha$ -ADA vector into the CD34+ cells from bone marrow *ex vivo*, we do not anticipate that they can enter the germ cells.

### **9.2.4 Allergic/immunological responses to cell processing excipients**

Stem Cell Factor (SCF) and thrombopoietin (TPO) are used to maintain stem cell viability and to promote gene transfer during the *ex vivo* transduction process. When these factors are administered parenterally, they may have untoward immunologic or allergic consequences such as thrombocytopenia or allergic reactions. The CD34+ cells cultured in these cytokines are thoroughly washed following *ex vivo* exposure. Since small amounts of residual factors

may remain, it is possible that the presence of these, and other cytokines used during the transduction process, may result in an adverse immunologic or allergic event. This hypothetical complication has not been reported from any of the clinical trials using these factors for *ex vivo* transduction.

### **9.2.5 Other adverse clinical consequences**

Participation in this protocol may have deleterious effects on subsequent attempts at allogeneic HSC transplantation. These adverse effects could be due to "immunisation" to normal human ADA produced from the transgene. Most patients however, will have received bovine PEG-ADA, which is more likely to be immunogenic than human ADA; the development of significant inhibitory antibodies has been relatively rare in patients treated with PEG-ADA alone. It is possible that non-PEGylated human ADA could be more immunogenic or its expression in cells could induce more T cell responses than injected recombinant protein. Additionally, this protocol could lead to restoration of partial immunity, insufficient for complete protection from infections and yet sufficient to increase the risks of rejections of allogeneic cells. This partial immunity may also result from PEG-ADA alone, although it may be possible to eradicate this residual activity by complete PEG-ADA cessation. For patients who have not received PEG-ADA the gene transfer procedure would introduce these risks *de novo*, although it is difficult to know *a priori* the potential likelihood of these hypothetical risks.

As with any new form of therapy, there may be risks which are unknown or not anticipated.

## **10 Name description of the IMP and critical raw materials**

### **10.1 Name and description of each IMP**

- EF1 $\alpha$ S-ADA lentiviral vector transduced patient CD34+ cells is designated as an IMP
- The IMP is patient-specific and corresponds to autologous CD34+ cells transduced *ex vivo* with the EF1 $\alpha$ S-ADA lentiviral vector containing the human ADA gene in final formulation and container closure system, ready for intended medical use
- In this study EF1 $\alpha$ S-ADA lentiviral vector is designated as a critical raw material
- The starting materials used for the production of the IMP consist of the viral vector and the patient's CD34+ cells

### **10.2 Production, supply and release of the IMP**

- Transduction of autologous CD34+ cells with the lentiviral vector will be carried out in the Gene Therapy Laboratory, Camelia Botnar laboratories, Great Ormond Street Hospital for Children NHS Trust.
- The transduced cells will be packaged in sealed transfer bags prior to being transported to the ward at Great Ormond Street Hospital (GOSH) for administration.
- An independent Qualified Person (QP) will be responsible for importation, sign off and release of the vector for use in the study

### **10.3 IMP accountability**

IMP accountability is ultimately the responsibility of the Chief Investigator. This responsibility however will be delegated to the Clinical Scientist responsible for the transduction procedure.

Detailed records will be kept to allow for accurate accountability of the vector and transduced CD34+ cells. These records will include details of shipping, receipt, storage, use and destruction of the vector. Transfer of CD34+ cells from the gene therapy laboratory to the ward at GOSH and administration of the transduced CD34+ cells to patients will be recorded.

### **10.4 Description and justification of the trial treatment and dosage**

The EF1αS-ADA lentiviral vector is used to transduce autologous CD34+ cells *ex vivo*. These transduced cells are then infused into the patient. The cell/product dose will consist of at least  $0.5 \times 10^6$  CD34+ cells per kg of body weight transduced *ex vivo* with  $1 \times 10^8$  i.g./ml of lentiviral vector to achieve an average of 0.3-2 integrated copies per cell. A higher dose would be expected but given that there is a survival advantage to gene corrected cells, this lower level has been designated as final release threshold in this study. This is supported by evidence gained from our first retroviral ADA trial here at GOSH, where two patients reconstituted effectively, having received less than  $0.5 \times 10^6$  transduced CD34+ cells/kg (Gaspar et al., 2011).

### **10.5 Dose modifications**

A single dose of cells will be administered to the patient and the dose is individual to the patient since the gene-modified cells are the IMP.

## **10.6 Assessment of compliance**

There is no compliance issue with IMP administration since gene modified cells are infused through a Hickman line and the infusion is monitored by a trained nurse.

## **10.7 Post-trial IMP arrangements**

There is no provision to provide patients with IMP post-trial participation.

## **10.8 Name of each NIMP**

- Cotrimoxazole
- Itraconazole
- Penicillin
- Aciclovir
- Immunoglobulin
- Calcium Folinate
- Busulfan

NIMP suspected Adverse Drug Reactions (ADR) or side effects will be reported through the yellow card system.

# **11 Recording and reporting of adverse events and reactions**

## **11.1 Definitions**

### **Adverse event**

This is defined as any untoward medical occurrence in the patient administered an IMP that does not necessarily have a causal relationship with this treatment.

### **Adverse reaction**

This is defined as any untoward and unintended response in a subject to an IMP, which is related to any dose administered to that subject.

### **Serious adverse event**

A serious adverse event is defined as any untoward medical occurrence in the patient administered an IMP, which does not necessarily have a causal relationship with this treatment, and that at any dose:

- Results in death
- Is life threatening
- Results in persistent or significant or disability/incapacity
- Requires in-patient hospitalisation or prolongs existing hospitalisation
- Results in a congenital abnormality or birth defect

Medically significant (i.e. any event which the investigator considers significant but which is not covered by the above)

### **Suspected Serious Adverse Reaction (SSAR)**

This is defined as an adverse reaction that is classed in nature as serious and which is consistent with the information about the IMP in question as set out in the Investigator's Brochure.

### **Suspected Unexpected Serious Adverse Reaction (SUSAR)**

The definition of a SUSAR is a serious adverse drug reaction, the nature or severity of which is not consistent with the applicable product information (as set out in the Investigator's Brochure) or which adds significant information on the specificity or severity of an expected event.

## **11.2 Recording adverse events**

All adverse events (related to the IMP, unrelated to the IMP, serious or not) will be recorded in the hospital notes and in the electronic Case Report Form (eCRF). An adverse events log may be adopted for the hospital notes.

If the investigator suspects that the disease has progressed faster due to the administration of the IMP, then he will report this as an unexpected adverse event to the sponsor.

Clinically significant abnormalities in the results of objective tests may also be recorded as adverse events.

The record of adverse events will include the following:

- **Clinical symptoms:** A simple, brief description
- **Severity:** we will categorise according to WHO classification (see appendix 7)
- **Causality assessment (relationship to treatment):** The assessment of relationship of adverse events to the administration of IMP is a clinical decision based on all available information at the time of the completion of the case report form. The following categories will be used:

Definitely: There is clear evidence to suggest a causal relationship, and other possible contributing factors can be ruled out.

Probably: There is evidence to suggest a causal relationship, and the influence of other factors is unlikely.

Possibly: There is some evidence to suggest a causal relationship (e.g. the event occurred within a reasonable time after administration of the trial medication). However, the influence of other factors may have contributed to the event (e.g. the patient's clinical condition, other concomitant events).

Unlikely: There is little evidence to suggest there is a causal relationship (e.g. the event did not occur within a reasonable time after administration of the trial medication). There is another reasonable explanation for the event (e.g. the patient's clinical condition, other concomitant treatments).

Not related: There is no evidence of any causal relationship.

Not Assessable

*Note: events assessed as possibly, probably or definitely related to the IMP are considered adverse reactions (ARs)*

- **Expectedness evaluation:** The following categories will be used:

Expected: An adverse event which is consistent with the information about the IMP listed in the Investigator Brochure or clearly defined in this protocol

Unexpected: An adverse event which is not consistent with the information about the IMP listed in the Investigator Brochure

- **Seriousness:** as defined for an SAE in section 11.2.1.

Collection, recording and reporting of adverse events (including serious and non-serious events and reactions) to the sponsor will be done according to the sponsor's SOP.

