#### ***Blood and the lymphatic system disorders:***

Myelo-suppression and immuno-suppression were the desired therapeutic effects of the conditioning regimen. Therefore all patients experienced profound cytopenia: leukopenia 96%, thrombocytopenia 94% and anemia 88%. The median time to neutropenia was 4 days for both autologous and allogeneic patients. The median duration of neutropenia was 6 days and 9 days for autologous and allogeneic patients.

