## Appendix 7: WHO classification of acute/subacute toxic effects

ITEM	Grade 1 Toxicity	Grade 2 Toxicity	Grade 3 Toxicity	Grade 4 Toxicity
HEMATOLOGY				
Hemoglobin	9.5 - 10.5 gm/DL	8.0 - 9.4 gm/DL	6.5 - 7.9 gm/DL	< 6.5 gm/DL
Absolute Neutrophil Count	1000-1500/mm 	750-999/mm 	500-749/mm 	<500/mm 
Platelets	75000-99000/mm 	50000-74999/mm 	20000-49000/mm 	<20000/mm 
Prothrombin Time (PT)	1.01 - 1.25 x ULN	1.26-1.5 x ULN	1.51 -3.0 x ULN	>3 x ULN
Activated Partial Thromboplastin (APPT)	1.01 -1.66 x ULN	1.67 - 2.33 x ULN	2.34 - 3 x ULN	> 3 x ULN
Fibrinogen	0.75 - 0.99 X LLN	0.50 - 0.74 x LLN	0.25 - 0.49 x LLN	< 0.25 x LLN
Fibrin Split Product	20-40 mcg/ml	41-50 mcg/ml	51-60 mcg/ml	> 60 mcg/ml
Methemoglobin	5 - 9.9 %	10.0 - 14.9 %	15.0 - 19.9%	> 20 %
LIVER ENZYMES				
AST (SGOT)	1.25 - 2.5 x ULN	2.6 - 5 x ULN	5.1 - 10 x ULN	> 10 x ULN
ALT (SGPT)	1.25 - 2.5 x ULN	2.6 - 5 x ULN	5.1 - 10 x ULN	> 10 x ULN
GGT	1.25 -2.5 x ULN	1.6 - 5 x ULN	5.1 - 10 x ULN	> 10 x ULN
Alkaline Phosphatase	1.25 - 2. 5 x ULN	1.6 - 5 x ULN	5.1 - 10 x ULN	> 10 x ULN
Amylase	1.1 - 1.5 x ULN	1.6 - 2.0 x ULN	2.1 - 5.0 x ULN	> 5.1 x ULN
CHEMISTRIES				
Hyponatremia	130-135 mEq/L	123-129 mEq/L	116-122 mEq/L	< 116 or mental status changes or seizures
Hypernatremia	146-150 mEq/L	151-157 mEq/L	158-165 mEq/L	> 165 mEq/L or mental status changes or seizures
Hypokalemia	3.0 - 3.4 mEq/L	2.5 - 2.9 mEq/L	2.0 - 2.4 mEq/L or intensive replacement Rx required or hospitalization required.	< 2.0 mEq/L or paresis or ileus or life-threatening arrhythmia
Hyperkalemia	5.6 - 6.0 mEq/L	6.1 - 6.5 mEq/L	6.6 - 7.0 mEq/l	> 7.0 mEq/L or life-threatening arrhythmia
Hypoglycemia	55-64 mg/dL	40-54 mg/dL	30-39 mg/dL	<30 mg/dL or mental status changes or coma
Hyperglycemia (note if fasting)	116 - 160 mg/dL	161- 250 mg/dL	251 - 500 mg/dL	> 500 mg/dL or ketoacidosis or seizures
Hypocalcemia (corrected for albumin)	8.4 - 7.8 mg/dL	7.7 - 7.0 mg/dL	6.9 - 6.1 mg/dL	< 6.1 mg/dL or life threatening arrhythmia or tetany
Hypercalcemia (correct for albumin)	10.6 - 11.5 mg/dL	11.6 - 12.5 mg/dL	12.6 - 13.5 mg/dL	> 13.5 mg/dL life-threatening arrhythmia

Hypomagnesemia	1.4 - 1.2 mEq/L	1.1 - 0.9 mEq/L	0.8 - 0.6 mEq/L	< 0.6 mEq/L or life-threatening arrhythmia

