#### 8.4.1.2 Adverse Events

Treatment emergent adverse events will be summarised for each of the IMP treated groups in an overall summary presenting the number (%) of subjects with:

- any AE,
- moderate or severe AE,
- severe AE,
- treatment related AE (possibly/probably/definitely/not assessable/missing),
- AE leading to study withdrawal,
- any serious adverse event (SAE),
- treatment related SAE,
- SAE leading to death.

Incidence and frequency of treatment emergent AEs will be summarised for each of the IMP treated groups by system organ class (SOC) and preferred term (PT):

- overall,
- by maximum severity,
- by maximum relationship to treatment,
- treatment related AEs,
- AEs leading to study withdrawal (if sufficient events).

In addition, a summary table for the most frequently reported treatment emergent adverse events (those reported in 2 or more subjects) will be presented by PT in descending order of incidence and frequency.

In each table, if the same SOC or PT is reported on multiple occasions for a single subject, it will only be included once in the summary. In the table by maximum severity, only the most severe occurrence for each SOC and PT for each subject will be included in the summary. In the table by maximum relationship, only the most related occurrence for each SOC and PT for each subject will be included in the summary.

Any adverse events that are not treatment emergent (occurred prior to the infusion) will be listed.

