### **8.4.1.3 Serious Adverse Events and Death**

Incidence and frequency of treatment emergent SAEs will be summarised for each of the IMP treated and HSCT control groups (data permitting) by system organ class (SOC) and preferred term (PT):

- overall,
- by maximum severity,
- by maximum relationship to treatment,
- treatment related SAEs.

In each table, if the same SOC or PT is reported on multiple occasions for a single subject, it will only be included once in the summary. In the table by maximum severity, only the most severe occurrence for each SOC and PT for each subject will be included in the summary. In the table by maximum relationship, only the most related occurrence for each SOC and PT for each subject will be included in the summary.

Any SAEs that are not treatment emergent (occurred prior to the infusion) will be listed.

If there are any deaths, the details will be listed.

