### **8.4.4 Laboratory Evaluations**

#### **8.4.4.1 Haematology**

Haematology parameters (red blood cell (RBC) count, haemoglobin, haematocrit, mean corpuscular volume (MCV), mean corpuscular haemoglobin (MCH), mean corpuscular haemoglobin concentration (MCHC), white blood cell (WBC), neutrophils, lymphocytes,

monocytes, eosinophils, basophils and platelet count) will be evaluated over time for the IMP treated subjects. The baseline evaluation for each parameter will be the final evaluation prior to the IMP infusion.

For each parameter, the actual value and change from baseline will be summarised at each visit using descriptive statistics for each of the IMP treated groups.

Haematology evaluations will be flagged against the normal range as low/normal/high. For each parameter, the number (%) of subjects with evaluations that were low/normal/high relative to the normal range will be summarised by visit. In addition, shift tables will be constructed comparing the flags at the baseline evaluation with those at each post-infusion evaluation and the minimum and maximum evaluation post-infusion. Out of range values will be assessed for their clinical significance. The number (%) of subjects with any clinically significant abnormal values will be summarized by parameter at each visit and at any time post-infusion.

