#### **8.4.4.2 Biochemistry**

Biochemistry parameters (sodium, glucose, chloride, potassium, urea, creatinine, calcium, magnesium, phosphates, albumin, alkaline phosphatase, alanine transaminase (ALT), aspartate transaminase (AST), gamma glutamyl transferase (GGT), bilirubin, total protein) will be evaluated over time for the IMP treated subjects. The baseline evaluation for each parameter will be the final evaluation prior to the IMP infusion.

For each parameter, the actual value and change from baseline will be summarised for each IMP treated group at each visit using descriptive statistics.

Biochemistry evaluations will be flagged against the normal range as low/normal/high. For each parameter, the number (%) of subjects with evaluations that were low/normal/high relative to the normal range will be summarised by visit. In addition, shift tables will be constructed comparing the flags at the baseline evaluation with those at each post-infusion evaluation and with the minimum and maximum evaluation post-infusion. Out of range values will be assessed for their clinical significance. The number (%) of subjects with clinically significant abnormal values will be summarized by parameter at each visit and at any time post-infusion.

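### The SAP does not carry over the protocol's four-grade toxicity scale: AE severity rows have no mapping to it, and the laboratory shift tables put a slightly low value and a grade 4 value in the same cell

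*Protocol*

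**What the plan says.** **AE severity in the protocol.** For each adverse event, Protocol 11.2 states of severity: "we will categorise according to WHO classification (see appendix 7". The appendix, headed "Appendix 7: WHO classification of acute/subacute toxic effects", has four graded columns with numeric bands for most routine laboratory parameters. For neutrophils, grade 1 is 1000–1500/mm3 and grade 4 is below 500/mm3. For platelets, grade 1 is 75000–99000/mm3 and grade 4 is below 20000/mm3.

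**AE severity in the SAP.** The overall table in 8.4.1.2 has two severity rows: "moderate or severe AE" and, below it, severe AEs. The same section tabulates AEs by system organ class and preferred term at maximum severity, with the rule that "only the most severe occurrence for each SOC and PT for each subject will be included in the summary". Section 8.4.1.3 does the same for SAEs ("by maximum severity"). Neither section lists the severity categories. The SAP mentions neither the WHO scale, nor toxicity grades, nor Appendix 7.

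**Laboratory values in the SAP.** Section 8.4.4.1: "Haematology evaluations will be flagged against the normal range as low/normal/high". Section 8.4.4.2: "Biochemistry evaluations will be flagged against the normal range as low/normal/high". Shift tables are built on these flags, including those for the lowest and highest post-infusion results. Both sections also plan observed values and changes since baseline at each visit, and counts of children with clinically significant abnormal values per visit and at any time. Under SAP section 8, the descriptive statistics include minimum and maximum.

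**The concern.** The SAP's severity words belong to a mild/moderate/severe scale, whereas the protocol records four grades. If the database follows the protocol, the SAP's rows cannot be programmed without deciding which grades count as moderate and which as severe. In an open-label trial that decision belongs in the SAP.

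For laboratory values the protocol supplies graded bands, but the SAP classifies by three flags. A shift table from baseline to worst post-infusion value is the natural place to see depth of toxicity, and three flags remove depth.

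Safety is half of the primary objective. Tolerability of conditioning is a secondary objective, left to review by the PI and study team and without a dedicated SAP analysis, so the AE and laboratory tables are its only statistical summary.

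**Working it through.** The documents state no figure on this point, so there is nothing to reproduce. The check sets the sections side by side and adds one illustration.

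**1. AE severity categories.** The eCRF severity field is not in the documents. There are two possibilities.

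| eCRF holds | Overall table (8.4.1.2) | Maximum-severity tables (8.4.1.2, 8.4.1.3) |
|---|---|---|
| Grades 1–4, as Protocol 11.2 implies | Needs an unstated mapping: severe could be grade 3 alone or grades 3–4 | Could show grade 4, but this is not specified |
| Mild/moderate/severe | Programmable | Cannot show grade 4; the eCRF would depart from Protocol 11.2 |

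In neither case does the SAP specify a count of children with grade 3 or higher, or with grade 4.

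**2. Laboratory flags against grades.** The values are invented. The documents give no lower limit of normal for neutrophils, so 1500/mm3 is assumed.

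- Set A: ten values of 1400. Low: 10/10. Grade 4: 0/10. Minimum, median and mean: 1400.
- Set B: five of 1400 and five of 100. Low: 10/10. Grade 4: 5/10. Minimum 100; median (100 + 1400)/2 = 750; mean (5 × 1400 + 5 × 100)/10 = 750.
- Set C: nine of 1400 and one of 100. Low: 10/10. Grade 4: 1/10. Minimum 100; median 1400; mean (9 × 1400 + 100)/10 = 1270.

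The flag tables for A, B and C are identical. The by-visit statistics separate A from B. The minimum does not separate B (five children at grade 4) from C (one child), and no planned statistic is the count itself.

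The result for these values holds for any lower limit above 1400. With a limit from just above 100 up to 1400, set A would be 0/10 low and set B 5/10 low. The collapse itself remains for any limit above 500, because values from 500 up to the limit share a cell with grade 4 values.

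**3. Link to the protocol's own thresholds.** Protocol 4.1 defines absent marrow recovery at 6 weeks as ANC below 0.5 × 10^9/L or platelets below 20 × 10^9/L. Since 1 L = 10^6 mm3, these are 500/mm3 and 20000/mm3, exactly the Appendix 7 grade 4 cut-offs. A blood count is scheduled at 6 weeks, but no SAP table counts the children below either value.

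**4. Which parameters Appendix 7 can grade.** Of the five blood-count parameters in the schedule, three have bands (haemoglobin, neutrophils, platelets); total white cells and lymphocytes have none. Of the 12 scheduled biochemistry parameters, all but albumin have bands, reading the BUN band as urea. The bands have defects:

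- GGT and alkaline phosphatase: grade 1 is 1.25–2.5 × ULN and grade 2 is 1.6–5 × ULN, so 2.0 × ULN falls in both.
- Platelets: grade 3 ends at 49000 and grade 2 starts at 50000, leaving a gap.
- Several bands, such as sodium, potassium, phosphate and creatinine, mix laboratory limits with clinical criteria (seizures, arrhythmia, replacement treatment, dialysis).

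**5. What a grade 4 count would convey with 10 on-study children.** Exact (Clopper–Pearson) 95% limits are the 0.025 quantile of Beta(r, n−r+1) and the 0.975 quantile of Beta(r+1, n−r), with the lower limit 0 at r = 0:

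- 0/10: 0% to 30.8%
- 1/10: 0.3% to 44.5%
- 3/10: 6.7% to 65.2%
- 5/10: 18.7% to 81.3%

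The count would be descriptive and imprecise.

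**The case against.** The strongest reply is that severe toxicity is visible elsewhere. Maximum-severity tables cover AEs and SAEs, and could show grade 4 if the eCRF holds grades. A neutrophil count of 100 would appear as a visit minimum. Life-threatening events meet the SAE definition, and marrow aplasia beyond one month is named among the expected serious events. Protocol 8.9.2 provides by-subject listings as appropriate, readable with 10 children. All of this stands, and it limits the point.

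Three stronger inferences are therefore not supported:

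- A reader might infer that AEs are counted solely in the two overall rows and that grade 4 is lost. The maximum-severity tables contradict the first part, and the second cannot be settled without the eCRF.
- A reader might infer that mild and extreme laboratory values look alike throughout the output. That is true of the flag and shift tables, not of the by-visit statistics.
- A reader might apply the 96% leukopenia and 94% thrombocytopenia rates in Appendix 6 and expect nearly every child to be flagged low. Those are adult rates of ever having the event. The same appendix gives a median of 4 days to neutropenia and, in autologous patients, 6 days' duration, whereas scheduled post-infusion counts start at 1 month ± 5 days. The rates do not describe the SAP's tables.

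What the reply leaves unanswered is the number of children at each grade. A minimum gives one worst value per visit. Clinical significance has no stated threshold. An SAE is not the same as a grade 4 event. Protocol 11.2 makes it optional to record a laboratory abnormality as an AE, so the AE tables cannot be relied on to fill the gap.

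**Conclusion.** The point holds in limited form. The SAP's AE severity categories are not reconciled with the scale the protocol prescribes, and the laboratory shift rule discards the grade bands that the protocol supplies. No table is specified that counts children reaching grade 3 or 4. The gap is in tabulation, not in the data the protocol calls for, and it does not touch the survival comparisons.

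This rests on the SAP text as it stands and on the eCRF following Protocol 11.2. If the eCRF uses mild/moderate/severe instead, the discrepancy lies between eCRF and protocol and must be resolved there first. It is a low-cost improvement to the safety reporting of a small trial, where a count of grade 4 events is easier to interpret than a flag.

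**What to change.** **SAP 8.4.1.2 and 8.4.1.3.** Define severity as Appendix 7 grades 1–4 and tabulate AEs and SAEs by maximum grade, with subject counts for grade 3 or higher and for grade 4. If the moderate and severe rows are kept, state which grades each contains. For the HSCT controls, state which scale applies, because Protocol Appendix 8 lists AEs and SAEs to be collected without naming one.

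**SAP 8.4.4.1 and 8.4.4.2.** Keep the low/normal/high tables. Add shifts from baseline grade (including below grade 1) to worst post-infusion grade for collected parameters with Appendix 7 bands, such as haemoglobin, neutrophils, platelets, ALT, bilirubin, creatinine and electrolytes. Total white cells and lymphocytes cannot be graded this way and stay with the existing summaries.

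**Before programming.** Resolve the GGT and alkaline phosphatase overlap and the platelet gap, specify the numeric part of each mixed clinical/laboratory band, and convert units where the site's differ.

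**Cost.** SAP wording and programming, with no new data if the eCRF follows Protocol 11.2. More grade 3–4 toxicity will be visible. Worst grades drawn from scheduled visits may still miss an early nadir, so the laboratory shifts complement the graded AE tables and do not replace them.
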